#### Sponsor or funding source: Departmental

#### **Background, Rationale and Context**

Postoperative pain management has become an area of concern over the last decade due to the opioid epidemic and concerns that the use of opioids as a primary pain management strategy in the post-operative period may promote misuse or abuse of opioids in the outpatient setting (Hah, Bateman, Ratliff, Curtin, and Sun, 2017; Alam, Gomes, Zheng, Mamdani, Juurlink & Bell, 2012). As of January 1, 2018, The Joint Commission requires hospitals to have non-pharmacologic modalities available for pain management in an effort to decrease the need for opioids. Acupuncture and acupressure have been used for centuries in the management of a variety of disorders including pain. A recent meta-analysis (Zhong et al., 2019) of 26 RCTs (all included studies were in China) favored the use of acupressure for pain management over usual care based on total effective rate (RR =1.25, [CI= 1.13, 1.37], p < .0001) and total analgesia use (RR=0.41, [CI=0.24, 0.68] p = .0006). There were no serious adverse events reported in the 26 trials (N=1063 in treatment groups) and no withdrawals from the studies were reported due to adverse events. Unlike acupuncture, acupressure can be easily applied with training and is within the scope of practice for nurses, according to the North Carolina Board of Nursing (NCBON, 2013). Although acupressure has been used for centuries in traditional Chinese medicine, there are few studies assessing the use of nurse initiated acupressure in hospital settings as an adjuvant to postoperative pain management.

Battlefield acupuncture (BFA) was developed by [name], a U.S. Air Force radiation oncologist. BFA utilizes 5 acupoints that are thought to be involved in central processing of pain. [name] protocol has been used in the United States military in the treatment of pain for over 15 years. In the last few years, the Veterans Administration in conjunction with the Department of Defense has expanded BFA training to providers within the VA system (Walker, et al., 2016). A cross sectional study of 753 patient BFA encounters (284 individual patients) within the West Haven VA Medical Center, found that patients receiving BFA showed on average a 2 point decrease in pain scores (measured on a 0-10 scale) with each BFA encounter ( $p \le .001$ ) (Federman et al., 2018). More recently, in an effort to increase access to non-pharmacological modalities for pain management, the VA has developed a battlefield auricular acupressure (BAA) protocol. The BAA protocol uses the same acupoints as the BFA protocol but instead of piercing the skin with needles to stimulate the acupoints, tiny beads or seeds are placed on the sites and stimulation of the sites is achieved when manual pressure is applied to the seed. The advantage of BAA is that since it does not require needles, patients may tolerate or be more open to its use, application of the seeds or beads is within the scope of practice of registered

The purpose of this pilot is to test the feasibility of nurse initiated post-operative battlefield auricular acupressure as an adjunct to medication for post-operative pain management.

## **Objectives**

1. To determine if battlefield auricular acupressure applied in the immediate pre-operative period improves post-operative pain management related to:

Protocol version: 5 50CT2020 Template updated 9.24.14

- a. total opioid intake over 5 days
- b. aggregated mean pain score over 5 days
- c. acceptability of auricular acupressure as pain management tool
- 2. To determine the feasibility of nurse initiated battlefield acupressure related to nurse time, cost and perceptions related to auricular acupressure and workflow.

## Methods and Measures

#### Design

• Randomized controlled trial.

Setting

Davie Medical Center

#### Subjects selection criteria

## Inclusion Criteria

Adults 18-80 admitted for knee or hip arthroplasty. Pre-surgery morphine equivalent < 50, ASA score < 3

## • Exclusion Criteria

Participants with a history of skin disease (e.g., psoriasis) involving the ear, adhesive allergy, latex allergy, recent scar tissue on ear, or current abrasions or cuts on ear, history of delirium, or cognitive impairment. Some hearing aids may prevent proper placement of acupressure pads and thus, require exclusion. Since this is a feasibility pilot, only English speaking participants will be eligible.

# Sample Size

Based on previous published literature, we estimate a total sample size of 48 -52 needed (24-26 each arm) to detect a 30% difference in pain scores or 25% reduction in analgesia. Recruitment target will be 30 in each arm (N=60) to allow for attrition. In order to identify the 60 subjects needed, we may need to screen as many as 120 because some people will not qualify to be included in the study.

## **Interventions and Interactions**

Terms: AA = Auricular acupressure

Acupressure pad= hypoallergenic adhesive pad containing a 2 mm Vaccaria seeds (Earseeds®) Acupoint = specific area of body where acupressure is applied. BAA= Battlefield Auricular Acupressure

The three regional anesthesia nurses at Davie will be trained to deliver the intervention. All three nurses have been CITI trained and for this protocol will be referred to as auricular acupressure (AA) nurses. In addition to the three AA nurses, CTSI will provide study coordination.

• Training of the AA nurses for auricular acupressure will be done by the Wake Forest Center for Integrative Medicine (CIM) providers. Training will have both didactic and hands-on practice components: basic concepts of auricular acupressure, anatomy and physiology of the ear, assessment of ear anatomy, proper identification of therapeutic acupoints, proper cleaning of the ear, application of acupressure pads and activation, and patient education related to activation of the acupressure pads with manual pressure. Competency will be assessed both by assessment of knowledge (written assessment) and direct observation by CIM acupuncturist of the AA nurse's ability to correctly identify auricular acupressure points through visual inspection, proper application of acupressure pads and activation of the acupressure applied to the acupressure pads.

- Participants will be informed of the study at the time of their surgical consult with their physician or at their pre-operative appointment via flyers made available to the surgical clinics. Prior to the pre-assessment visit, study personnel will review the chart of patients who express interest in the study to confirm eligibility. Informed consent will be obtained at the pre-operative assessment visit by study personnel and the participant questionnaire will be reviewed with instructions on the day of surgery, the AA nurse will confirm consent for participation. Random assignment will be generated by REDCap and emailed to the AA nurse by the study coordinator. If participant is assigned to treatment, the acupressure pads will be placed in the pre-operative holding room. The participant's designee will be given the study questionnaire packet as well as instructions for completing.
- AA nurses will record time from the moment they enter participant's room in holding room for the purposes of placing acupressure pads and activating each pad until they exit room. AA nurses will make notation if recorded time includes activity unrelated to placement of acupressure pads. After placement of acupressure pads, AA nurse will enter procedure note in WakeOne and complete the REDCap nurse questionnaire.
- **Treatment Group**: The AA nurses will place the acupressure pads on the participant preoperatively while the participant is in the PACU using the following BAA protocol:
  - Before acupressure pad placement, pain assessment will be performed and recorded in the study chart by the AA nurses. AA nurse will also ensure that a responsible family member is in the pre-operative holding room with participant to listen to instructions.
  - Acupressure pads will be placed prior to any amnesic or pain medication.
  - AA nurse will have participant don surgical cap, being careful to keep all hair under the cap.
  - If the ear contains lesions, skin breakdown, or show signs of irritation, the acupressure pads will not be placed and this will be noted in the study record.
  - A total of 10 adhesive acupressure pads will be placed, 5 acupressure pads per ear. The pads will be placed bilaterally on the following 5 auricular sites: 1)
    Cyngulate gyrus, 2) Thalamus, 3) Omega 2 4) Point Zero, and 5) Shen Men. These sites were selected based on the WV's Battlefield Auricular Acupressure Protocol for acute and chronic pain. This is the protocol the Veterans Administration uses for acupressure therapy for acute and chronic pain management and is taught to both nurses and physicians. Each ear will be cleansed with alcohol, beginning at the base of the ear (lobule) to the apex. The acupoints will be visually located and marked with a sterile surgical marker. The pads will be placed by visual identification of the preselected acupoints as per BAA protocol. The pads will be placed on the on the identified site by hand or with the assistance tweezers, with the seed portion of the pad aligning with the identified acupoint. To secure the pad, gentle but firm pressure will be applied to the pad, making sure that pressure is applied to the entire pad.
  - After placement, the study nurse will apply moderate pressure to each acupressure pad for 30 seconds (total time 2.5 minutes per ear). Both right and left ear site will be stimulated at the same time with pressure in the following order: 1) Cyngulate gyrus, 2) Thalamus, 3) Omega 2, 4) Point Zero, and 5) Shen Men Participants will tell the AA nurse when they feel a tingling sensation in the ear or feel moderate tenderness or pressure as confirmation that moderate pressure is being applied.

- The AA nurse will document in WakeOne acupressure pad placement and activation.
- Once participant is transferred to the floor, the AA nurse will review with participant and family how and when to activate each pad and give participant or designee a picture of a right and left ear with the acupressure pads in place with pads labeled 1-5. Participants will be reminded to gently press on each pad for 30 seconds three times a day to activate and to do this three times a day for a total of 5 days (roughly every 6-8 hours, while awake during the day). The provided picture will be used by the participant to account for any missing pads on the participant questionnaire. If the participant requests, the AA nurse will take a picture with the participant's smartphone of the participant's ears with the pads in place. The study questionnaire will also direct participants to apply moderate pressure using thumb and forefinger to each pad for 30 seconds each three times a day.
- If acupressure pads fall off while the participant is still in the hospital, the participant and/or nursing staff will be instructed to call the AA nurse on call for replacement of the pads prior to discharge.
- Participants may stimulate both ear sites at the same time beginning with site 1 and ending with site 5. Studies have placed acupressure pads for 3-8 days depending on study outcomes (He et al., 2013; Yeh et al., 2014), the pads will be placed for a total of 5 days based on manufacturer's recommendation and the BAA protocol (See example of Earseeds instruction brochure). On the day of surgery, the participant will be informed to apply pressure one to 2 more times that day, depending upon the time the acupressure pads were placed. Participants will be informed that if any acupressure pads fall off while home, they are not to be replaced, but to record on the study questionnaire (see participant questionnaire). Staff nurses will remind participants to complete their questionnaires and to call the AA nurses with any questions related to the acupressure pads or the study.
- At time of discharge, the study personnel will ensure that the participant has participant questionnaire and the addressed and stamped envelope. Instructions for activation of the acupressure pads and questionnaire completion will be reviewed. Participants will be informed that they will either receive a phone call or text reminder twice daily to complete the questionnaire and to activate their pads 3 times per day. Participant is to continue to apply pressure to remaining pads until the end of the study.
- On post-operative day 4, the study personnel will call the patient and instruct them to remove the acupressure pads by gently pulling on the edges of the pad and lifting off with their fingers or using tweezers to loosen the pad if needed. Participants will be reminded to mail questionnaire in the provided postage paid envelope, if they have not done so already
- **Control Group:** The AA nurse will give participants in the control group the study questionnaire once they arrive to the floor and remind participant and family to complete the questionnaire as indicated. At time of discharge, study personnel will ensure that participant has study questionnaire and the addressed and postage paid envelope. Participants will be informed that they will either receive twice daily phone calls or text messages to complete the questionnaire. On postoperative day 4, study personnel will call and remind participate to mail questionnaire in the provided postage-paid envelope.

• Contact information will be obtained at time of study enrollment/consent in order to remind participants daily to complete study document. The reminders will be via telephone call by study personnel and/or via text messaging depending on participant preference. Participants may also be contacted to complete the final questionnaire over the phone if the document if this section is incomplete when received by the study team.

| Ambulatory
Appointment | Preoperative
Assessment | Day of
Surgery | Recovery
Rm        | PO-
0       | PO-
1       | PO-
2 | РО-
3       | PO-
4       |
|---------------------------|----------------------------|-------------------|-----------------------|----------------|----------------|----------|----------------|----------------|
| Study flyer               | Study flyer                |                   | O 1 | O 2 | O 3 | $O_4$    | O 5 | $O_6$          |
|                           |                            | R                 | Х                     | Х              | Х              | Х        | Х              | Х              |
|                           | Informed                   | Informed          | O1                    | O 2 | O 3 | O4       | O5             | O 6 |
|                           | Consent                    | Consent           |                       |                |                |          |                |                |

Note: O= Observation; R = Randomization, X = Acupressure pellet placement and/or activation with manual pressure.

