## **Outcome Measure(s)**

- 1) Pain: Both inpatient and outpatient pain scores will be measured using the VAS as documented on the participant study questionnaire.
  - a. am pain score on rising aggregated over 4 days (post-op day 1 –post-op day 4)
  - b. pm (worse pain throughout the day) pain score aggregated over 5 days (post-op day 0 post-op day 4)
  - c. trajectory of am and pm pain scores
- 2) Inpatient opioid pain medication will be collected via the MAR in WakeOne. Outpatient usage will be self-reported in study questionnaire. Inpatient and outpatient total opioid use will be converted to total Morphine equivalent.
  - a. Total morphine equivalent aggregated over day 0-4
  - b. Trajectory of morphine equivalent from day 0 4
- 3) Overall participant satisfaction will be measured on post-op day 4 via participant questionnaire.
- 4) Nurse time will be measured in minutes from time AA nurse enters room to place acupressure pads to when AA nurse exits room. Qualitative questions will be used to assess overall feasibility of nurse initiated auricular acupressure.

| Outcome               | Measure         | Baseline | Post-op Day 1-2 | Post-op days
1-4 |
|-----------------------|-----------------|----------|-----------------|---------------------|
| Pain                  | Visual Analogue | X        |                 | Х                   |
|                       |                 |          |                 |                     |
| Medication            | WakeOne MAR     |          | Х               | Χ                   |
| Inpatient             | Participant     |          |                 |                     |
| -                     | Questionnaire   |          |                 |                     |
| Medication Use | Participant     |          |                 | Х                   |
| Outpatient            | Questionnaire   |          |                 |                     |
| Pellet Retention      | Participant     |          | X               | X                   |
| Days                  | Questionnaire   |          |                 |                     |
| Pain                  | Participant     |          |                 | Х                   |
| Management            | Questionnaire   |          |                 |                     |
| satisfaction          |                 |          |                 |                     |

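### A Baseline pain VAS is planned without arm limit, but the procedures describe a pre-treatment pain assessment only in the acupressure arm, so a comparable control baseline is not assured

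*Combined protocol and SAP*

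**What the plan says.** **Outcome Measure(s), table.** The columns begin "Baseline | Post-op Day 1-2" and the pain row reads "Visual Analogue | X", so a Baseline VAS is planned. Nothing restricts it to one arm. The text above the table says that pain is measured by VAS on the participant questionnaire. The listed pain outcomes are all post-operative: a morning score over post-op days 1 to 4, a "pm (worse pain throughout the day) pain score aggregated over 5 days" (days 0 to 4), and the trajectories of both.

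**Interventions and Interactions, Treatment Group.** "Before acupressure pad placement, pain assessment will be performed and recorded in the study chart by the AA nurses". The instrument is not named, and the record is the study chart rather than the questionnaire.

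**Interventions and Interactions, Control Group.** The paragraph starts after surgery: "The AA nurse will give participants in the control group the study questionnaire once they arrive to the floor". It mentions no earlier pain rating.

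**Shared pre-operative steps** (opening part of Interventions and Interactions, Subject Recruitment Methods, Informed Consent). These cover screening, consent, review of the questionnaire and random assignment. None mentions a pain score.

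**Schedule table.** O1 appears in both observation rows, under the recovery room column, which follows the Day of Surgery column holding R. The key reads "Note: O= Observation; R = Randomization, X = Acupressure pellet placement and/or activation with manual pressure" and does not say what O1 measures.

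**Analytical Plan.** It lists descriptive statistics, between-group tests and multilevel models for pain and morphine equivalents over time. No baseline covariate is named.

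**The concern.** The outcome table and the narrated procedures do not match. The table promises a Baseline score for the trial as a whole. The procedures describe how to obtain a pre-treatment score in one arm only, as part of pad placement. Staff who work from the narrated steps alone could miss it in controls.

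A baseline held in one arm only cannot be compared between arms or used for adjustment. Two things would be lost: the precision that a prognostic covariate brings to the pain comparison, and the ability to show, or adjust for, a chance difference in pre-operative pain between two small groups. There is also a smaller gap. The outcome text puts pain scores on the questionnaire VAS, while the treatment-arm assessment goes in the study chart with no instrument named. Even that score is not clearly the planned Baseline.

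**Working it through.** **1. Is O1 the baseline?** Two readings are open.

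- *O1 is the baseline.* O2 to O6 already cover post-op days 0 to 4, which are all the pain days among the listed outcomes, so a further recovery-room score would feed none of them. The O1 column also carries an X (placement and/or activation), and the Treatment Group text places pads "preoperatively while the participant is in the PACU using the following BAA protocol", so the plan itself uses a recovery-area name for a pre-operative step.
- *O1 is a post-operative recovery score.* Elsewhere the same section puts placement in the pre-operative holding room. The column follows Day of Surgery and R, and X may mean activation only.

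The first reading explains more of the table. Neither is stated.

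**2. What would a common baseline be worth?** The Sample Size section gives 24-26 evaluable per arm and a recruitment target of 30 per arm. It gives no alpha, sidedness, power or SD, so its figure cannot be reproduced. Assumed here: two-sided alpha 0.05, 80% unadjusted power, and a range for the baseline-outcome correlation r.

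The standardised difference d that gives exactly 80% power (noncentral t, 2n-2 df) is 0.826 at n = 24, 0.792 at n = 26 and 0.736 at n = 30.

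With the baseline as covariate:
- adjusted effect = d / sqrt(1 - r²), with 2n-3 df;
- to allow for average chance imbalance, the residual variance is also multiplied by 1 + 1/(2n-4), which is 1 + 1/44 = 1.023 at n = 24.

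Example at n = 24, r = 0.3: 0.826 / sqrt(0.91) = 0.866, or 0.866 / sqrt(1.023) = 0.856 with the penalty.

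| r | Power, n = 24 | Power with imbalance penalty |
|---|---|---|
| 0.1 | 80.4% | 79.5% |
| 0.2 | 81.5% | 80.7% |
| 0.3 | 83.5% | 82.7% |
| 0.4 | 86.3% | 85.6% |
| 0.5 | 89.9% | 89.2% |
| 0.6 | 93.8% | 93.3% |

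The first power column differs by no more than 0.1 point at n = 26 or 30.

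**3. How likely is a chance imbalance?** The SE of the difference in baseline means is sqrt(2/n) SD: 0.289, 0.277 and 0.258 at n = 24, 26 and 30. By the normal approximation, the chance that the arms differ by more than 0.5 SD is 8.3%, 7.1% and 5.3%.

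An imbalance of 0.5 SD shifts the unadjusted pain difference by 0.5 × r SD: 0.05 SD at r = 0.1, 0.15 SD at 0.3 and 0.30 SD at 0.6. Against d = 0.826 these are 6%, 18% and 36%.

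**The case against.** The strongest reply is that the outcome table and the schedule are as much part of the plan as the narrated steps. The Baseline mark has no arm limit and O1 is in both rows, so staff following the schedule would record O1 in controls too. If O1 is the baseline under a wrong room label, what remains is mainly labelling and timing. The shared text in Interventions and Interactions also has the questionnaire reviewed with participants, and a packet handed to the designee with no arm stated. Appendix 1, the form that carries the pain VAS, was not available and could settle the matter.

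Most of this stands. A reader might infer that controls will have no baseline at all; the documents do not support that. They support only that a control score is not assured: neither questionnaire sentence mentions a baseline rating, the control paragraph hands the form over on the floor after surgery, and O1 is undefined.

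Two other strong readings also fail. One is that the Baseline score has no use. The descriptive statistics and group comparisons in the Analytical Plan can cover it; only a covariate role is unstated. The other is that a missed control score is lost for good. The documents do not say whether a usable pre-operative score exists in the hospital record.

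It is also fair that this is a feasibility pilot and that the gain rests on an assumed correlation. That limits the severity. It does not remove the mismatch.

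**Conclusion.** The point holds as a gap in specification. The plan calls for a Baseline pain VAS without arm limit, describes a pre-treatment assessment only for the acupressure arm, and leaves O1 undefined. Up to 30 planned controls are affected, unless O1 or Appendix 1 supplies their score.

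A reader might go further and conclude that the treatment comparison is biased. It is not: post-operative scores compared between randomised arms need no baseline to be unbiased, and no listed outcome is a change from baseline. The loss is in precision and in the handling of chance imbalance. Under the assumptions above, adjustment is worth nothing at a correlation of 0.1, about 3 points of power at 0.3 and about 13 at 0.6, for the pain comparison only. Severity is moderate to low. The case for acting is that the change is cheap.

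**What to change.** 1. Move the pain assessment out of the Treatment Group list. Take one VAS from every participant in pre-operative holding when the AA nurse confirms consent, before the REDCap assignment is released. The rating is then made without knowledge of arm.
2. Define this score as the Baseline in the outcome table, and name the form. If Appendix 1 already has a baseline item, keep it and state that both arms complete it at this point.
3. Name it as a covariate in the pain models in the Analytical Plan.
4. State whether O1 is this baseline (if so, place it before R in both rows) or a separate post-operative score. Reconcile PACU, recovery room and holding room across the placement text, the Treatment Group list and the schedule.

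**Cost.** One short rating for about 30 controls, at a contact with the AA nurse that the plan already describes. The assignment email waits briefly for the score and must still leave time for the plan's own sequence: "Acupressure pads will be placed prior to any amnesic or pain medication". That is tightest for participants who consent on the day of surgery. The rating should be noted separately so that it does not enter the nurse-time outcome; the plan already has nurses flag activity unrelated to pad placement. The rest is wording.

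### Questionnaire hand-over and completion instructions are described differently for the two arms, although pain and outpatient opioid use are self-reported on that questionnaire

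*Combined protocol and SAP*

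**What the plan says.** All of the procedural text is in the protocol's Interventions and Interactions section.

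- **Both arms, before surgery.** A run-on sentence says "the participant questionnaire will be reviewed with instructions on the day of surgery, the AA nurse will confirm consent for participation". It is not limited to an arm. It leaves open whether the review takes place at the pre-operative visit or on the day of surgery.
- **Pads, then packet.** The text continues: "If participant is assigned to treatment, the acupressure pads will be placed in the pre-operative holding room". The next sentence reads: "The participant's designee will be given the study questionnaire packet as well as instructions for completing". Only the first of these two is limited to the treatment arm; the second states neither arm nor time.
- **Treatment arm.** Before pad placement the nurse must "ensure that a responsible family member is in the pre-operative holding room with participant to listen to instructions". Later treatment text has staff nurses prompt participants to fill in the form. At discharge, personnel check that the participant holds it and go over both pad activation and questionnaire completion.
- **Control arm.** "The AA nurse will give participants in the control group the study questionnaire once they arrive to the floor". The nurse also reminds participant and family to complete it. At discharge there is a check that the participant holds the form, but no review of how to complete it.

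The Outcome Measure(s) section makes this form the pain instrument: "Both inpatient and outpatient pain scores will be measured using the VAS as documented on the participant study questionnaire". Outpatient opioid use is also self-reported on it. Inpatient opioids are taken from the medication administration record.

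**The concern.** Controls receive no sham, so participants know their assignment, and the main outcomes rest on what they write down. In such a trial the collection of self-reports should be the same in both arms, except where the treatment itself requires a difference. Teaching pad activation must differ by arm; teaching someone to complete a pain and medication diary need not.

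As written, one arm may get the form and its instructions before surgery through a designee, while the other gets it on the ward. One arm also has a further completion review at discharge. Either difference could lead to more complete or differently scored entries in one arm, and the analysis could not separate that from a treatment effect. The outpatient opioid entries feed the total morphine equivalent over days 0 to 4, so the question is not confined to pain.

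**Working it through.** The protocol gives no figure on this point to reproduce. The check sets the two arms' text side by side and then counts the outcomes within reach.

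**1. Steps by arm**

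| Step | Treatment | Control |
|---|---|---|
| Review of questionnaire before surgery | Yes (arm not stated) | Yes (arm not stated) |
| Hand-over | Only the designee sentence can apply; time not stated | By the AA nurse, on the floor |
| Family involvement | Family member required in the holding room | Family reminded on the floor |
| AA nurse visit on the floor | Yes, about pad activation | Yes, about the questionnaire |
| Staff-nurse prompts to complete | Stated | Not stated |
| Check at discharge that form is held | Yes | Yes |
| Completion instructions reviewed at discharge | Yes | Not stated |
| Twice-daily reminders, day-4 call | Yes | Yes |

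**2. The two readings of the designee sentence**

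- If it applies to the treatment arm, as its position suggests, hand-over differs by arm in time and recipient.
- If it applies to everyone, controls have two different hand-over descriptions, and the text must be reconciled.

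Both readings call for the same edit.

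**3. Outcomes that hand-over timing can reach**

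- Morning pain is described as "am pain score on rising aggregated over 4 days", days 1 to 4: 4 scores.
- Evening (worst of the day) pain, days 0 to 4: 5 scores.
- Total listed: 4 + 5 = 9 scores, none of them from the recovery room.
- Recorded on the day when hand-over could differ: 1 of 9 (1 of the 5 evening scores), the day-0 evening score.
- Outpatient opioid use and day-4 satisfaction: recorded after both arms have been checked for holding the form, so timing does not reach them.
- Inpatient opioids: not on the form.

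**4. Illustrative size for the day-0 evening score**

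The inputs here are assumptions; the documents give none. Let day-0 pain be higher than the later days by e = 1 to 2 points, on a 0–10 scale. Let the day-0 entry be missing more often in controls by 10 to 20 percentage points, and let the aggregate be the mean of available scores.

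- Losing day 0 lowers a participant's five-day mean by e/5: 1/5 = 0.2 to 2/5 = 0.4 points.
- Shift in the control mean: 0.2 × 0.10 = 0.02 to 0.4 × 0.20 = 0.08 points.

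In this direction the control mean falls, which works against showing a benefit. Nothing in the documents fixes the direction.

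**5. Outcomes that unequal completion instruction can reach**

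The discharge review and the staff-nurse prompts bear on entries made afterwards, including outpatient opioid use. The documents offer no basis for sizing this.

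**The case against.** The best counter-argument is that this is loose drafting rather than a planned difference. Much of it stands.

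- A reader might infer that the treatment arm's designee definitely receives the packet before surgery. That is the natural reading in sequence, but the sentence does not say so.
- A reader might infer that controls are first instructed soon after anaesthesia. The documents do not support this: the earlier questionnaire review is not limited to an arm, and consent and its confirmation both precede surgery.
- A reader might infer that the recovery-room observation (O1 in the schedule) can be recorded on the diary in one arm only. The schedule defines O simply as an observation, does not tie O1 to the questionnaire, and no listed outcome uses a recovery-room score. What O1 measures is unclear for both arms alike.
- The family contrast is weaker than it looks. The holding-room requirement is a pad-placement step that does not mention the questionnaire, and the control paragraph also involves the family.
- Later contacts are largely parallel: a floor visit, a discharge check, twice-daily reminders and a day-4 call in both arms.

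Two things survive. The hand-over is not described in the same way for both arms on either reading, and the discharge review of completion instructions appears in the treatment text only.

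**Conclusion.** The point holds as a minor one: an avoidable, probably small difference in how self-reports are set up, or else an inconsistency about controls that needs resolving. The timing component is confined to one of nine listed pain scores. The 0.02 to 0.08 point figure shows only an order of magnitude, since the day-0 excess, the differential missingness and the scale are all assumed. The instruction component could extend to later pain entries and outpatient opioid use, but its size and direction cannot be derived from the documents. None of this shows that the trial's comparison is biased; it shows that the protocol leaves room for a difference that is easy to remove.

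**What to change.** In Interventions and Interactions, edit the general day-of-surgery text and the Control Group paragraph so that they agree:

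1. State one hand-over time for both arms, before surgery.
2. Name the same recipients in both arms: the participant and the designee.
3. Use one script for completing the questionnaire, with pad-activation teaching kept as a separate, treatment-only item.
4. Add to the Control Group paragraph the questionnaire-completion review at discharge that the treatment text already has, and state that staff-nurse prompts to complete the form apply to both arms.

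The day-of-surgery consent confirmation by the AA nurse is a possible occasion for the hand-over. The protocol does not say where it takes place, so the location should be written in. The existing floor visits can stay as they are. The cost is a wording change and a few minutes of staff time per control participant.
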